Participants will be randomized into four groups using urn randomization, a covariate adaptive randomization method (Wei & Lachin, 1988). Adaptive randomization is employed because it protects the study from bias while promoting study objectives, it improves power over standard designs, and it balances assignment of treatment across covariates in a way superior to traditional stratification (Rosenberger et al., 2012). We aim to achieve balanced groups on three main child covariates: age, gender, and ethnicity. An advantage of the Mauritius cohort is that we have data on the parents' externalizing behavior over the life-course (Raine et al. 2010) which we could add as a fourth covariate to further ensure that groups are balanced.

Omega-3 Intervention

Omega-3 supplementation. As in the pilot study, this consists of a 200 ml drink. The base drink in both treatment and placebo conditions consists of fruit juice containing vitamin D (0.85 micrograms) and antioxidants (ferric reducing ability of plasma value of 0.71 mmol/100g). For the treatment condition only, 1660 mg of omega-3 (550 mg of DHA, 550 mg of EPA, 560 mg of alpha-linolenic acid) is added to the base drink. Placebo drinks are matched exactly with the fish-oil drink in terms of size, appearance, and flavor. Caregiver and child drinks are differentially color-coded.

This drink is chosen because: (i) it contains a higher dosage of omega-3 than standard capsules in a small liquid quantity (60.6% of a standard can of cola) suitable for child / adolescent consumption, (ii) the fruit-flavored drink may be better tolerated and result in higher compliance with children than fish-oil capsules.

Treatment duration and administration. As in the pilot study, treatment duration will be six months. It was chosen because prior studies have usually been 2 - 4 months (Sinn et al., 2010), and a longer duration may be more effective in producing longer-term behavioral change. The drink will be administered by the parents to their children at any time each day.

Primary Outcome Measures

The pre-defined primary outcome measures are externalizing behavior problems. Secondary outcomes included internalizing behavior problems and neurocognitive / academic mediators. We include additional *secondary* measures of reactive-proactive aggressive behavior and callous-unemotional traits to replicate the pilot findings and explore antisocial subtypes (the pilot data showed stronger effects for reactive aggression).

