Externalizing and internalizing behavior problems in children and caregivers will be assessed using the Multicultural Family Assessment Module (MFAM - Achenbach et al., 2015) which constitutes counterpart scales of the Child Behavior Checklist (CBCL/6-18), Youth Self-Report (YSR), Adult Self-Report (ASR), and Adult Behavior Checklist (ABCL). Reliability, validity, and cross-cultural generalizability have been documented in over 100 societies (Achenbach & Rescorla, 2001; Achenbach & Rescorla, 2001; Rescorla et al., 2012). The Externalizing scale includes Aggressive Behavior and Rule-Breaking Behavior, while the Internalizing scale includes Anxious/Depressed, Withdrawn, and Somatic Complaints. Additional syndromes include Attention Problems, Social Problems, and Thought Problems. Instruments are also scored on DSM-oriented scales comprising items judged by international clinical experts to be very consistent with DSM diagnostic criteria.

Adolescents will rate themselves on the Youth Self-Report YSR. The caregiver will rate their child on the CBCL/6-18, themselves on the ASR, and their spouse on the ABCL. We have established measurement invariance of the CBCL in this cohort in Mauritius (Yarnell et al., 2013). Teacher ratings of the child will be assessed using the Teacher Report Form of the MFAM. In consultation with [name] (Consultant), we will adopt the same system he has used in his national surveys to successfully obtain individual-based teacher ratings using payment to the teacher with a parental permission letter (Achenbach & Rescorla, 2001).

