Aims 1 and 2 (Primary Outcome). These hypotheses will be addressed using adolescent and caregiver externalizing responses gathered at baseline and at 6, 12, and 18 month follow-ups. Responses for the adolescent will be analyzed separately from responses for the caregiver. For each separate set of responses, linear mixed effects models (Molenberghs & Verbeke, 2005) will be used to describe both the pattern of response and the within-subject covariance structure across time points. Primary analyses will not include baseline covariates, as the randomization will balance the treatment groups and eliminate selection bias. To enhance power by controlling for variability in response (Kahan et al., 2014), a small set of baseline covariates (e.g. gender, age, ethnicity) will be included in supplementary analyses.

The response may be transformed (e.g. log transformation) to reduce levels of skewness in the response to acceptable levels, as assessed by examination of residuals. Models will include binary indicators for adolescent group (omega-3 vs placebo), caregiver group (omega-3 vs placebo), and time (four level factor for times 0, 6, 12, and 18), and group by time interaction terms, as fixed effects. Time is modeled as a discrete factor to accommodate the patterns observed in our prior study (see Figure under Preliminary Data) where the omega-3 adolescent groups are similar at baseline and 6 months, and separate at 12 months. Covariance structure models (e.g. random effects, autocorrelated residuals) will be compared using information criteria in models containing all main effects and interactions of interest. Once the covariance structure has been chosen, the fixed effects will be assessed for significance using likelihood ratio tests.

Parameter estimates, standard errors, and 95% confidence intervals will be reported. In the case of a multiple degree of freedom test (e.g. group by time interaction, with 3 df), single-df contrasts will be estimated and reported, to explain the nature of the interaction.

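### The interaction-then-main-effect rule gives about 9.75% false positives at an assumed 0.05 per step, its fallback averages in the pre-treatment visit, and the text names no deciding child form

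*Combined protocol and SAP*

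**What the plan says.** All references are to the combined protocol and SAP.

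- **Outcome.** Under Primary Outcome Measures: "The pre-defined primary outcome measures are externalizing behavior problems". Child externalizing is then collected on three forms: the YSR, which the adolescent completes; the CBCL/6-18, from the caregiver ("The caregiver will rate their child on the CBCL/6-18, themselves on the ASR, and their spouse on the ABCL"); and the TRF, from the teacher ("Teacher ratings of the child will be assessed using the Teacher Report Form of the MFAM").
- **Model.** Under Statistical Methods, Aims 1 and 2: "Responses for the adolescent will be analyzed separately from responses for the caregiver". Time is a four-level factor that includes month 0. Fixed effects are assessed by likelihood ratio tests.
- **Decision rule.** Hypothesis 1a is judged on the child-group-by-time interaction or, when that is non-significant, on the child-group main effect. Hypothesis 1b uses similar models for the caregiver. Hypothesis 2a, for both sets of responses, uses the three-way interaction with time, or the two-way group interaction if trends are parallel.
- **Baseline.** Under Randomization: "We aim to achieve balanced groups on three main child covariates: age, gender, and ethnicity". Parental externalizing is mentioned only as a possible fourth factor. Under Statistical Methods: "Primary analyses will not include baseline covariates"; adjusted models are supplementary.
- **Error rate.** No significance level, sidedness or multiplicity rule is given. The nearest text is that 95% intervals will be reported.

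**The concern.** The rule gives each hypothesis two chances to succeed, each presumably at the full level, so its false-positive rate is close to twice the level of either step.

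The fallback also has a structural fault. Treatment cannot act at month 0, so a real effect makes the group trends non-parallel. A gap that is truly constant over all four visits was there before treatment. A main effect averaged over months 0, 6, 12 and 18 therefore dilutes a genuine effect and admits a chance baseline difference as evidence. Child externalizing is not among the three named balancing factors and its baseline value is not a covariate in the primary model, so nothing else in the primary analysis removes such a difference.

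Separately, the text does not say which child form, or what combination of forms, decides the adolescent result. If that is settled after the data are seen, the error rate rises again.

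**Working it through.** **Inputs.** From the document: 400 pairs, 100 per cell, so 200 v 200 for each factor; visits at 0, 6, 12 and 18 months; interaction 3 df, main effect 1 df. Assumed: two-sided 0.05 per step; within-person correlation ρ of 0.3–0.7, compound symmetry (CS) or AR(1); cross-form correlations as shown. The document gives no alpha, power, effect size or SD, so there is no error rate or power of its own to reproduce. The cell count checks: 4 × 100 = 400.

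**1. False positives on one score.** The interaction test and the main-effect test in the reduced model are nested, hence asymptotically independent under the null. The rule rejects with probability 1 − (1 − 0.05)(1 − 0.05) = 1 − 0.9025 = 9.75%. Simulation gives 9.7–9.8% under CS and AR(1). Finite-sample likelihood ratio tests give 10.1% at n = 400 and 9.7% at n = 368 (8% attrition). At level a per step the rate is 1 − (1 − a)².

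**2. Allowance for the urn.** Balancing on covariates that the model omits makes the main-effect step conservative. If they are perfectly balanced and explain a share R² of person-mean variance, its true level is 2[1 − Φ(1.96/√(1 − R²))].
- R² = 0.05: 0.0443, so the rule gives 1 − 0.95 × 0.9557 = 9.2%.
- R² = 0.10: 8.7%. R² = 0.20: 7.7%.
- R² = 0.30: 0.0191, so the rule gives 1 − 0.95 × 0.9809 = 6.8%.

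**3. What the fallback estimates.** The generalized least squares weights on months 0, 6, 12 and 18 are 0.25 each under CS. Under AR(1) they run from 0.29/0.21/0.21/0.29 (ρ = 0.3) to 0.385/0.115/0.115/0.385 (ρ = 0.7).
- Effect at months 12 and 18: 0.25 + 0.25, or 0.115 + 0.385, = 50% recovered.
- Effect at month 12 only: 12–25% recovered.

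**4. A chance baseline gap with no treatment effect.** The standard error of a baseline difference is √(2/200) = 0.10 SD, so 0.2 SD is 2 standard errors. Given that gap, the two-step rule is significant 32–42% of the time and the interaction alone 9–14%. Under simple randomization a gap that large in either direction has probability of about 4.6%.

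**5. Choice of form.** If any of three forms may count under the two-step rule, the rate is 24%, 21% and 16% at cross-form correlations of 0.5, 0.7 and 0.9.

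**6. Power of the replacements.** Take 0.28 SD, 200 v 200, ρ = 0.5. With no true difference at month 0, the 4-df joint test (group plus group-by-time) and the 3-df joint test of months 6, 12 and 18 with month-0 means constrained equal have the same noncentrality, (200/2) × d′V⁻¹d. The constrained test uses one df fewer.
- CS: V⁻¹ = 2I − 0.4J. Effect at two visits: 100 × 0.0784 × (4 − 1.6) = 18.8. At three visits: 100 × 0.0784 × (6 − 3.6) = 18.8.
- AR(1): two visits, 100 × 0.0784 × 1.25/0.75 = 13.1; three visits, 100 × 0.0784 × 1.5/0.75 = 15.7.

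| Test | Effect at 12, 18 (CS / AR(1)) | Effect at 6, 12, 18 (CS / AR(1)) |
|---|---|---|
| Two-step rule as written | 96% / 86% | 96% / 92% |
| Interaction alone, 3 df | 93% / 72% | 83% / 70% |
| Joint group + group-by-time, 4 df | 95% / 84% | 95% / 91% |
| Joint months 6, 12, 18, baseline constrained, 3 df | 97% / 87% | 97% / 93% |

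The last three tests hold 5%; the two-step rule does not. Given the 0.2 SD baseline gap, the 4-df test rejects when 4 + χ²₃ exceeds 9.49, that is 14% of the time. The constrained test conditions on baseline and stays at 5%.

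**The case against.** Several stronger readings are tempting, and the documents do not support them.

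- A reader might infer that Hypothesis 1a itself names no form. Its wording is not in the document, which cites the hypotheses by label only. What can be said is that the outcome and analysis sections name none. The reference to adolescent responses may mean the self-report YSR, although it also fits reports about the adolescent.
- A reader might take 9.75% as the trial's actual rate. It rests on an assumed alpha, and step 2 shows that it is nearer an upper figure for one score.
- With three forms and zero correlation the rate would be 26.5%. Ratings of the same child are unlikely to be uncorrelated, and the visits at which the TRF is collected are not separately stated.
- The 32–42% in step 4 is not additional error. It is conditional on an uncommon gap and is already contained in the 9.75%. It shows the mechanism only.
- It might seem enough to delete the fallback. That would cost up to 22 points of power (92% to 70%), and most of the loss is avoidable with a joint test.

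The supplementary covariate-adjusted models and the optional fourth balancing factor help somewhat, but neither alters the primary decision rule. The two-step rule is written out in full, and its error rate exceeds the per-step level at every R² considered.

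**Conclusion.** The decision rule is wrong as written. At an assumed two-sided 0.05 per step it gives about 9.75% false positives on a single score, or about 9.2% to 6.8% if the balanced but unadjusted covariates explain 5–30% of person-mean variance. This holds even if the adolescent outcome is read as the YSR alone, and it applies to 1a, 1b and 2a. The fallback averages in a visit at which no effect can exist.

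The unnamed child form is a separate and lesser gap. It takes the rate to roughly 16–24% only if any of the three forms may count, at assumed correlations of 0.9–0.5. The error-rate finding needs only the stated rule and the per-step level. The power figures also depend on the assumed effect size, correlation and covariance structure.

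**What to change.** Before unblinding, amend the SAP wording.

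1. **One test per hypothesis.** Replace the two-step rule for 1a, 1b and 2a with a single test at a stated two-sided 0.05. Preferred: a 3-df joint test of the group effect at months 6, 12 and 18, keeping baseline in the model as a response and constraining the group means at month 0 to be equal, which randomization justifies. Alternative: the 4-df joint test of group plus group-by-time. For 2a, apply the same test to the child-by-caregiver-group terms.
2. **Benefit.** Pre-specify the single-df contrast and direction that define benefit, and state what is concluded when the joint test is significant but that contrast is not. This will arise: with an effect at months 12 and 18, 16% (CS) or 22% (AR(1)) of significant 3-df interaction results had a non-significant month-12 contrast.
3. **Score.** Name one child externalizing score, or one composite, collected at all four visits, and make the other forms secondary. The choice is the sponsor's. The document says of the CBCL "We have established measurement invariance of the CBCL in this cohort in Mauritius", but its rater is also randomized, so if it is named, report the YSR beside it.
4. **Hierarchy.** State which of the 1a, 1b and 2a tests are primary, with a multiplicity rule if there is more than one.

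**Cost.** Results on the other forms become secondary, and there is a little more analysis wording. No new data are needed if the named score is collected at every visit. The preferred test costs no power against the two-step rule in the cases tabulated. A multiplicity adjustment would cost some: for example, Holm over four tests (1a, 1b, and 2a on each set of responses) starts at 0.05/4 = 0.0125, where a single-df test with 80% power at 0.05 has about 62%.

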Unique Protocol ID: JCHP-2

Brief Title: Omega-3 Supplementation to Both Parent and Adolescent

Official Title: Omega-3 Supplementation to Both Parent and Adolescent to Reduce Behavior Problems

Document Date: May 16, 2018

Experimental Design and Methods

This section provides the design and method of the overarching study within which the three aims will be tested. We also briefly specify further programmatic goals of this line of study, and also how the specific expertise of the research team will help ensure feasibility. As with the pilot study, methodology and ultimately reporting of results will follow CONSORT 2010 guidelines (Moher et al., 2010).

Design Overview

The study design will consist of a stratified, double-blind, placebo-controlled, factorial, randomized controlled trial of children and their caregivers in a community sample in Mauritius. This closely follows the design of the pilot study (Raine et al. 2015). Unlike the pilot study however, it will utilize a 2x2 factorial design, in which children *and* their parents will be randomly assigned to either omega-3 supplementation (treatment condition) or a placebo (control condition), and will have an extended follow-up at 18 months. This results in 4 groups: (1) child and caregiver both receiving omega-3, (2) child receives omega-3, caregiver receives placebo, (3) caregiver receives omega-3, child receives placebo, (4) both parent and child receive placebo. Assessments will take place at 0 months (baseline), 6 months (end of supplementation), 12 months (6 months post-treatment), and 18 months (12 months post-treatment).

Background To The Sample and the Mauritius Child Health Project

Adolescents and caregivers will be drawn from the Mauritius Child Health Study, a multi-generational study involving three generations of subjects. Details of these three generations are provided in a cohort profile (Raine et al. 2010). Originally set up by [name] (Consultant), this longitudinal study covers early child health and development and the identification of early risk factors (including nutrition) for later psychopathology, as well as early primary prevention. Early factors that shape later cognitive functioning have also been a focus. Given the pilot findings and longitudinal data on the parents, it provides a unique platform on which to build.

Participants, Potential Attrition, and Strategies to Deal with Attrition

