Participants will consist of 400 pairs of children and their caregivers (total N = 800). This replicates cell sizes in the pilot data and allows close comparability, with 100 children and 100 adults in each of four cells. The caregivers consist of the second generation participants (their parents are the first generation) who originally comprised the birth cohort. Their adolescent children are the third generation. All caregivers have previously participated in the Mauritius Child Health Project (Raine et al., 2010). Adolescents will be aged between 11 and 18 years old, willing to participate in an RCT, and residing in the community. Exclusion criteria consist of: (1) allergy to fish or fish products, (2) use of fish oil supplementation in the past six months, (3) intellectual disability, (4) participation in the prior RCT. There are currently 1,126 children aged 11-18 years actively participating in the Mauritius Child Health Project (51.2% female; 73.2% Indian, 24.5% Creole, 2.3% other), 124 of whom took part in the prior RCT and will be excluded. Written informed consent will be obtained from the parents with assent obtained from adolescents. The study will take place in interview rooms at the project headquarters in Quatre Bornes.

Attrition is an issue in all RCTs. In our pilot data however, attrition was only 8%, even after one year, and is likely attributable both to the long-standing intergenerational relationships between our research team in Mauritius and the participants. Attrition may nevertheless be slightly more with the longer follow-up. We have three strategies to deal with attrition. First, analyses will be intention-to-treat, including all participants regardless of drop-outs. Second, we will enhance participation using staggered incentives for completion. Third, we will code for missingness and assess whether it moderates treatment outcome.

Randomization

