The parent (CBCL) and youth (YSR) reports also include School Competence scales, while the teacher (TRF) form includes Academic Performance and Adaptive Functioning (Achenbach et al., 2015). These will extend the scope on mechanistic processes beyond neurocognitive functioning.

As in the pilot study, parental belief in treatment allocation to the omega-3 group (yes, no) will be measured at the end of treatment to assess influence on behavioral change. Demographics will again be collected on entry into the study, together with an adverse events questionnaire at the end of treatment.

Adherence to protocol and blood assays.

Adherence to the treatment regimen is a frequent problem in RCTs. As before, this will be assessed by assays of omega-3 from finger-prick blood taken from both caregiver and adolescent at all four time-points, with microwave irradiation assays conducted by team member [name] an NIAAA. For full methodological details see Lin, Loewke, Hyun, Leazer, & Hibbeln (2012). In response to C2, blood will additionally be assessed mid-way through supplementation (3 months). To help further enhance adherence, participants will be called every two weeks to remind them to use supplements, and to assess frequency of drink consumption by caregiver and adolescent in that time period (number of drinks / two weeks). To further facilitate compliance, participants will be given a bonus payment if their % blood omega-3 levels have risen higher than the bottom quartile of the population.

Statistical Methods

Overview. An intention-to-treat (ITT) design using all randomly assigned participants will be employed for all data analyses. All data will be blindly double-entered and checked for consistency.

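### Adverse events are asked about only at the end of treatment, and Somatic Complaints appears only inside Internalizing, so new symptoms on the drink may be under-detected; a baseline checklist and a separate Somatic Complaints report are cheap improvements

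*Combined protocol and SAP*

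**What the plan says.** The document is a combined protocol and SAP. Adverse-event collection is covered by one sentence under Secondary Outcome Measures: "Demographics will again be collected on entry into the study, together with an adverse events questionnaire at the end of treatment". The form's content, recall period, respondent and analysis are not described. The two-weekly telephone calls, under the adherence heading, cover reminders and drink counts; symptoms are not mentioned.

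Under Primary Outcome Measures, "the Internalizing scale includes Anxious/Depressed, Withdrawn, and Somatic Complaints". The same section gives the role of Internalizing: "Secondary outcomes included internalizing behavior problems and neurocognitive / academic mediators".

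Design Overview sets assessments at 0, 6, 12 and 18 months. Statistical Methods spells out that schedule for one behaviour score only: "adolescent and caregiver externalizing responses gathered at baseline and at 6, 12, and 18 month follow-ups". Externalizing and Internalizing are scored from the same family of forms, so Somatic Complaints at all four visits is a reasonable inference but not a stated fact.

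Statistical Methods describes no analysis of adverse events, and none of Somatic Complaints as a possible harm.

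**The concern.** A questionnaire first given after six months of the drink cannot show, for an individual, whether a complaint was there before the first drink. If the form records any current symptom, long-standing complaints enter both arms, shrink the visible difference and add variance. A real excess of new symptoms could then go unseen and the drink be reported as well tolerated.

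Somatic Complaints could supply a before-and-after measure of bodily symptoms in both recipients. Inside a three-part sum, however, a somatic rise is averaged with two scales that need not move the same way. The stake is modest but real: this is a daily supplement taken for six months by 11-18-year-olds and their caregivers, with a single described safety reading.

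**Working it through.** **Inputs from the documents.** There are four cells of 100 pairs: 4 × 100 = 400 pairs, and 400 × 2 = 800 people, which reproduces the stated total. For each generation, own drink is compared as 200 v 200. Pilot attrition was 8%, which would leave 200 × 0.92 = 184 per arm. The plan gives no adverse-event rate, alpha or power figure, so there is nothing further to reproduce.

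**Assumptions (not in the documents).** Two-sided 5% test. New symptoms in 2% (placebo) and 7% (omega-3) of those symptom-free at entry. A fraction b has the symptom at entry, and a fraction k of those still report it at month 6.

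**Step 1: month-6 reading only.** Prevalence in each arm is p = b·k + (1 − b)·new. Power is Φ[(d − 1.96·SE₀)/SE₁], where d = p₁ − p₀, SE₀ = √[2p̄(1 − p̄)/n] and SE₁ = √{[p₀(1 − p₀) + p₁(1 − p₁)]/n}.

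For b = 0.20, k = 1, n = 200:
- p₀ = 0.20 + 0.80 × 0.02 = 0.216; p₁ = 0.20 + 0.80 × 0.07 = 0.256; d = 0.040
- SE₀ = 0.0425; SE₁ = 0.0424
- power = Φ(−1.02) = 0.15

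**Step 2: with a baseline reading.** Only those symptom-free at entry are compared, n = 0.80 × 200 = 160 per arm, 0.02 v 0.07. SE₀ = 0.0232, SE₁ = 0.0230, and power = Φ(0.20) = 0.58.

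**Step 3: vary persistence (b = 0.20, n = 200).**

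| Prior symptoms reported at month 6 | Month-6 prevalence | Power, month 6 only | Power, with baseline |
|---|---|---|---|
| All | 21.6% v 25.6% | 15% | 58% |
| Half | 11.6% v 15.6% | 21% | 58% |
| A quarter | 6.6% v 10.6% | 30% | 58% |
| None (form records new onset only) | 1.6% v 5.6% | 57% | 58% |

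**Step 4: vary background (full persistence).** At b = 10%: 25% v 63%. At b = 30%: 11% v 52%. At b = 0 nothing is lost.

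**Step 5: other rates, with attrition.** At 184 per arm, new symptoms 5% v 15% and full persistence, power is 0.60 without and 0.86 with a baseline reading at 10% background, and 0.28 v 0.77 at 30%.

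**Step 6: Somatic Complaints inside Internalizing.** Assume three equally weighted standardized subscales with pairwise correlation r, and a somatic rise of 0.3 SD with no change in the other two. The sum has SD √(3 + 6r). At r = 0.5 the effect is 0.3/√6 = 0.12 SD. At 184 per arm the SE is √(2/184) = 0.104 SD, so power is 0.82 for the subscale alone and 0.22 for the sum (0.24 at r = 0.4, 0.20 at r = 0.6).

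If the other two subscales each improve by g SD, the sum moves by (0.3 − 2g)/√6. That is 0.04 at g = 0.10, zero at g = 0.15 and −0.04 at g = 0.20.

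**Step 7: precision of a baseline-adjusted contrast (200 per arm, equal variances).** Adjusted SE = √[(2/200)(1 − r²)] and change-score SE = √[(2/200)·2(1 − r)], where r is now the baseline to month-6 correlation. At r = 0.5: 0.087 v 0.100 SD. At r = 0.7: 0.071 v 0.077 SD. The change score is the fair comparator, because the planned mixed model already carries baseline as a level of time. The gain is small.

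**The case against.** A reader might infer that treatment-emergent symptoms will be swamped or cancelled. The documents do not support that, for these reasons:

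- **The comparison is unbiased.** The trial is randomized, double-blind and placebo-controlled, so background complaints fall equally on both arms in expectation. Sensitivity and individual attribution are at risk, not validity.
- **The form is unseen.** If it asks only about events since the first drink and is answered accurately, the baseline reading adds almost nothing (57% v 58%). The 15% figure needs every prior symptom to persist and be reported, which is the case most favourable to the fix.
- **Cancellation needs a particular pattern.** A 0.3 SD somatic rise cancels exactly only if the other two subscales together improve by the same amount, for example 0.15 SD each. Without offsetting improvement the signal is diluted, not cancelled.
- **Internalizing is given no expected direction.** It is listed as a secondary outcome, and Statistical Methods sets out no analysis specific to it. The planned likelihood ratio tests are non-directional, and nothing says the subscales will go unreported.
- **Somatic Complaints is not the only symptom scale.** The instruments also cover Anxious/Depressed, Attention Problems and Thought Problems. It is only the one named scale evidently about bodily symptoms. Its items are not listed, so its sensitivity to drink-related complaints is unknown.
- **Silence is limited evidence.** The text is a methods section, and a safety plan could exist elsewhere.

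All of this stands as a limit on the claim. What it leaves is that the only described adverse-events reading is at the end of treatment, its onset wording is unstated, and no harm analysis of Somatic Complaints is pre-specified.

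**Conclusion.** The point holds as a low-cost improvement to the detection of harm; it is not a flaw that biases a result. Treatment-emergent symptoms may be under-detected. Under the assumed 2% v 7%, 20% background and 200 per arm, month-6-only power runs from about 15% to 57%, depending on persistence and on what the form asks, against 58% with a baseline reading. With no background symptoms, or with a form that records new onset only, the loss is nil or negligible. Dilution of Somatic Complaints does not depend on background prevalence, but it does assume equal weights and a subscale correlation near 0.5. None of the event rates, persistence fractions, effect sizes or correlations comes from the documents.

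**What to change.** 1. Give the same adverse-events checklist at the existing baseline visit, before the first drink. Count as treatment-emergent any symptom reported at the end of treatment that was absent or milder at baseline. State the respondent and the recall period, and whether the form asks about onset.
2. Pre-specify Somatic Complaints (YSR for the adolescent, ASR for the caregiver) as a descriptive safety outcome, and report it beside Internalizing. Compare it by the recipient's own drink, adjusted for baseline, with a 95% confidence interval. Make month 6 the main time point. Months 12 and 18 are supporting only, because they fall 6 and 12 months after the drink has stopped. Confirm that the scale is collected at all four visits.

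Costs: item 1 adds one short form at a visit already planned, and may slightly prompt later reporting, equally in both blinded arms. If the forms are completed at all four visits, item 2 needs only analysis wording. It adds six comparisons (two recipients by three visits), to be read as safety estimates and not as confirmatory tests. Sample size and the primary analysis are unaffected.
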